**A Prospective, Randomized, Double-Blind, Parallel-Group, Placebo-Controlled Trial
Of Bupropion Hydrochloride Sustained-Release In The Treatment Of Sexual
Dysfunction In Men On Methadone Maintenance Therapy.**

Name of investigator: [name]
Institution : Department of psychological medicine
Faculty of Medicine
University Malaya
[name]
Malaysia
[name]

Name of sponsor : University Malaya
[name]
Malaysia
[name]

Study Product : Bupropion Hydrochloride Sustained-Release

Protocol Number : AY001

CONFIDENTIAL

This document is confidential and the property of [name] [name]. No part of it may be transmitted, reproduced, published, or used by other persons without prior written authorization from the author.

LIST OF ABBREVIATIONS

AE	Adverse effect
b.d	Twice per day
CGI-SF	Clinical Global Impression Scale adapted for Sexual Function
ECG	Electrocardiogram
HIV	Human immunodeficiency virus
IIEF-15	International Index of Erectile Function
ITT	Intention-to-treat analyses
MADRS, Malay	Montgomery-Åsberg Depression Rating Scale
M.I.N.I	Mini International Neuropsychiatric Interview
OTI	Opiate Treatment Index
WHOQoL-Brief, Malay version	World health organization Quality of Life-Brief Scale
Mal-GRIMS	Malay Version of the Golombok-Rust Inventory of Marital State
SAE	Serious Adverse Experiences

PROTOCOL SUMMARY

TITLE	Randomized, Double-Blind, Parallel-Group, Placebo-Controlled Trial Of Bupropion Hydrochloride Sustained Release In The Treatment Of Sexual Dysfunction In Men On Methadone Maintenance Therapy.
SHORT TITLE	RCT Bupropion SR in SD among MMT men
INVESTIGATOR	[name]
SYUDY PROTOCOL	AY001
Phase	Phase II
Study Center(s)	Single-center (University Malaya Medical Centre)
STUDY DESIGN	Randomized, Double-Blind, Placebo-Controlled Study.
OBJECTIVE	To assess the therapeutic effect of bupropion hydrochloride sustained-release in the treatment of sexual dysfunction in men on methadone maintenance therapy
NUMBER OF SUBJECTS	70 (35 for each arm)
Diagnosis and Main Inclusion Criteria	Adult had a diagnosis of opioid dependence base on Diagnostic and Statistical Manual of Mental Disorders, Fourth Edition (DSM-IV) criteria, who were experiencing constant sexual dysfunction for ≥ 4 weeks while taking a stable dose of methadone for ≥ 6 months.
TEST PRODUCT, DOSE, AND ROUTE OF ADMINISTRATION	Bupropion hydrochloride sustained-release (Wellbutrin SR) 150mg once a day for 7 days then 150mg twice a day for 35 days. Taken orally by the subjects.
DURATION OF SUBJECT PARTICIPATION AND DURATION OF STUDY	Subjects will be on study for up to 63 days Screening: up to 7 days(1 week) Treatment: 42days (6 weeks) Follow-up: 14 days (2 weeks) The total duration of the study is expected to be 24 months. 20months for subject recruitment and 4 months for final subject follow-up.
EFFICACY EVALUATIONS	
PRIMARY ENDPOINT	
 Change from baseline International Index of Erectile Function (IIEF-15) score.
SECONDARY ENDPOINTS	
 Mean improvement in scores on the Clinical Global Impression Scale adapted for sexual Function (CGI-SF) Mean improvement in scores on the Arizona Sexual Experience

	
Scale (ASEX)
 
 • Safety and Tolerability
OTHER EVALUATIONS	
 • Montgomery-Åsberg Depression Rating Scale (MADRS- Malay version) • Mini International Neuropsychiatric Interview (M.I.N.I), • Opiate Treatment Index (OTI) • World health organization Quality of Life-Brief Scale (WHOQoL-Brief, Malay version) , • Malay Version of the Golombok-Rust Inventory of Marital State (Mal-GRIMS) • Rapid urine drug test
SAFETY EVALUATIONS	Incidence of adverse events
STATISTICS Primary Analysis Plan	Data will be analyzed using linear mixed-effects model.

TABLE OF CONTENTS	Pg
LIST OF ABBREVIATIONS	3
PROTOCOL SUMMARY	4
INTRODUCTION	9
1. BACKGROUND	9
1.1 Investigational Agent	10
1.2 Overview of Non-Clinical Studies	10
1.3 Overview of Clinical Studies	11
1.4 Risk / Benefit Assessment	11
1.4.1 Dose Rationale	11
1.4.2 Potential Risk	11
1.4.3 Potential Benefit	11
1.4.4 Risk Benefit Ratio	11
2 STUDY RATIONALE	12
3 STUDY OBJECTIVES	12
3.1 Primary Objective	12
3.2 Secondary Objectives	12
4 STUDY DESIGN	13
4.1 Design	13
4.2 Procedure	13
4.3 Project Timetable	14
5 CRITERIA FOR EVALUATION	14
5.1 Primary Efficacy Endpoint	14
5.2 Secondary Efficacy Endpoints	14
5.3 Safety Evaluations	14
6 SUBJECT SELECTION	15
6.1 Study Population	15
6.2 Inclusion Criteria	15
6.3 Exclusion Criteria	15
6.4 Subject Recruitment and Screening	15
7 EARLY WITHDRAWAL OF SUBJECTS	16
7.1 When and How to Withdraw Subjects	16
7.2 Data Collection and Follow-up for Withdrawn Subjects	17
8 STUDY TREATMENTS	17
8.1 Method of Assigning Subjects to Treatment Groups	17

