3 STUDY OBJECTIVES

3.1 Primary Objective

- 3.1.1 To assess the clinical efficacy of bupropion hydrochloride sustained-release in the treatment of sexual dysfunction in men on methadone maintenance therapy.

Hypothesis

Bupropion hydrochloride sustained-release treated subjects will show significant improvement in Clinical Global Impression Scale adapted for Sexual Function (CGI-SF) then placebo treated subjects between baseline and week 6.

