5 CRITERIA FOR EVALUATION

5.1 Primary Efficacy Endpoint

The primary endpoint to be measured in this study is:

- CGI-SF at the baseline, day 14(week 2), day 28(week four) and day 42 (week 6).

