11 STATISTICAL PLAN

11.1 Sample Size Determination

For the hypothesis testing of this study, the significance level was set at 5%. The hypothesis involves comparison of 2 groups on the mean of a continuous outcome. Each group of 35 provides 90% power to detect an effect size of 0.5.

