Analyses of the Primary and Secondary Endpoints: The effect of Bupropion Hydrochloride Sustained-Release in improving the sexual dysfunction in the subjects is measured with CGI-SF at baseline, week 2, 4 and 6. The secondary outcomes are measured with IIEF15, its 5 domains and ASEX at baseline, week 2, 4 and 6. These repeated measurements will be analyzed using linear mixed-effects model. While these analyses are exploratory, they will provide useful information on differences in trends of reduction of depression and other outcomes between the Bupropion Hydrochloride Sustained-Release and placebo groups.

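### The Protocol Summary makes IIEF-15 the primary endpoint, the body makes it CGI-SF, and nothing says which prevails

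*Combined protocol and SAP*

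**What the plan says.** **Protocol Summary.** The primary endpoint is "Change from baseline International Index of Erectile Function (IIEF-15) score", with no time point and no statement of whether the total or a domain score is meant. The first secondary endpoint is "Mean improvement in scores on the Clinical Global Impression Scale adapted for sexual Function (CGI-SF").

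**Section 3.1.** The primary hypothesis is that men on bupropion will "show significant improvement in Clinical Global Impression Scale adapted for Sexual Function (CGI-SF") relative to placebo, from baseline to week 6.

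**Section 5.1.** The primary endpoint is "CGI-SF at the baseline, day 14(week 2), day 28(week four) and day 42 (week 6").

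**Sections 3.2 and 5.2.** The five IIEF-15 domains and ASEX are secondary. Section 5.2 lists no overall IIEF-15 score.

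**Section 11.1.** "For the hypothesis testing of this study, the significance level was set at 5" per cent. The outcome is described only as continuous, and sidedness is not given.

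**Section 11.2.** The effect of treatment is measured with CGI-SF, and then: "The secondary outcomes are measured with IIEF15, its 5 domains and ASEX at baseline, week 2, 4 and 6". The same paragraph adds "While these analyses are exploratory" and refers to "differences in trends of reduction of depression and other outcomes".

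**The concern.** The two versions are a complete exchange: each scale is primary in one place and secondary in the other. They are not interchangeable. CGI-SF is a global rating of sexual function. IIEF-15 is a questionnaire with five domains, of which erectile function is one. A trial can succeed on one and fail on the other.

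With both versions in the current protocol, either result could be reported as prespecified and the protocol could not be used to contradict it. The plan has no rule of precedence, no division of the 5% and no testing order. Section 11.2 assigns the analysis to the principal investigator, and section 19 makes the same role responsible for publishing the primary results. That implies no fault, but it means the document itself has to fix the choice.

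**Working it through.** **1. The passages side by side**

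| Place | CGI-SF | IIEF-15 | Time point or comparison |
|---|---|---|---|
| Protocol Summary | secondary | primary (score not specified) | none given |
| 3.1 and 3.2 | primary | secondary (domains) | baseline to week 6 |
| 5.1 and 5.2 | primary | secondary (domains only) | baseline, weeks 2, 4 and 6 |
| 6.4 | listed, not ranked | listed, not ranked | none given |
| 11.1 | not named | not named | none given |
| 11.2 | primary by implication | secondary (IIEF-15 and its domains) | baseline, weeks 2, 4 and 6; trends |

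In section 11.2 the word primary is not attached to CGI-SF. It follows from the paragraph heading, which covers primary and secondary endpoints, and from the next sentence, which calls the other scales secondary.

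**2. Can the sample size settle it?** Section 11.1 states 90% power with 35 per group for an effect size of 0.5. Read as a standardized difference in a simple two-group comparison, power is Φ(d√(n/2) − z), with d√(n/2) = 0.5 × √17.5 = 2.092.

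- Two-sided 5%: Φ(2.092 − 1.960) = Φ(0.132) = 55.2%.
- One-sided 5%: Φ(2.092 − 1.645) = Φ(0.447) = 67.2%.

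Neither reproduces 90%, so the calculation identifies neither the outcome nor the sidedness. The shortfall in power is a separate matter, and this point does not depend on it.

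**3. Error rate if the primary is chosen after the results.** Under the null, take two z-statistics with correlation r, each tested at 5%. The probability that at least one rejects is 1 − P(neither rejects), from the bivariate normal. At r = 0 this is 1 − 0.95² = 0.0975.

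| r (assumed) | Both two-sided 5% | Both one-sided 5% |
|---|---|---|
| 0 | 9.75% | 9.75% |
| 0.5 | 9.1% | 8.8% |
| 0.8 | 7.8% | 7.5% |
| 0.9 | 7.0% | 6.8% |

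The two-sided column counts rejections in either direction. Counting only those that favour bupropion, one two-sided test gives 2.5%. Choosing between two gives at most 1 − 0.975² = 4.9% (r = 0), and 3.5% at r = 0.9.

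**4. Error rate if only the body is followed.** There is one test on CGI-SF, so the rate is 5%.

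**The case against.** The strongest reply is that the Summary is simply out of date. Sections 3.1, 3.2, 5.1, 5.2 and 11.2 all agree, and only the Summary ranks IIEF-15 first. The Summary differs from the body elsewhere too: it gives 7 days at the starting dose where sections 8.3.2.2 and 8.6 give 3, and 20 months of recruitment where section 4.3 gives about 18. The title, the stated objective and the rationale all speak of sexual dysfunction. This makes CGI-SF the more likely intention, but it does not prove it. The Background (section 1) states the trial's aim as treating erectile dysfunction, and the one earlier bupropion study in methadone patients that the protocol describes reports an IIEF score (section 1.3). That evidence is limited. An erectile aim would point to the erectile function domain, which section 3.2.1 makes secondary, rather than to an overall score.

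Three further replies have force:

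- The visit list in 5.1 and the interval in 3.1 are compatible. What is missing is the model contrast that forms the primary test.
- The inflated error rates apply only if the endpoint is selected after the results, which no section plans. The two-sided figures are also not rates of false efficacy claims.
- Sidedness, the exploratory label, the absent IIEF-15 total and the reference to depression are separate defects. They do not add to the seriousness of this one.

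None of these removes the contradiction.

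**Conclusion.** The concern holds and must be fixed. The endpoint that decides the trial is stated in two incompatible ways, and no section resolves the conflict. The conclusion rests on the text alone, not on the error rates. Those rates show what is at stake: no inflation under the body's version, and 7.0% to 9.75% (two-sided) or 6.8% to 9.75% (one-sided) if the choice is made after the results, for correlations of 0.9 to 0. Two sexual-function scales in the same men are likely to be correlated, so 9.75% is an upper bound and not an expected value.

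**What to change.** Before unblinding, state one primary endpoint, one time point and one mixed-model contrast, in identical words, in the Summary and in sections 3.1, 5.1, 11.1 and 11.2.

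- **Smallest edit.** Align the Summary with the body: CGI-SF, baseline to week 6, tested for example as the treatment difference at week 6 from the linear mixed model. Another contrast would also serve if it is fixed in advance. List IIEF-15 (the overall score, if that is meant, and the five domains) as secondary in both the Summary and section 5.2.
- **If the sponsor intends IIEF-15.** Sections 3.1, 3.2, 5.1, 5.2 and 11.2 change instead, and the score (total or domain) must be specified.
- **Section 11.1.** Name the outcome to which the 0.5 effect size refers, with its justification for that scale, and say whether the 5% is one- or two-sided.
- **Section 11.2.** State whether the primary comparison is a formal test or exploratory, so that it agrees with 11.1; that choice is the sponsor's. Separately, correct the stray reference to depression.

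The cost is protocol wording, plus the effect-size justification. No further patients or data are needed: both scales are already scheduled at baseline and weeks 2, 4 and 6. The documents do not show what stage the trial has reached, so this assumes that the blind has not been broken.

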1. BACKGROUND

Sexual dysfunctions, such as reduced libido or arousal and impairments in erectile, ejaculatory and orgasmic functions, are commonly found in men among both the mentally ill as well as the healthy populations. The prevalence of sexual dysfunction among healthy men ranges from 20% to 35%, and in male populations with psychiatric illness, 50% to 65%. [1-5]

Methadone maintenance treatment (MMT) is a comprehensive treatment program that involves the long-term prescribing of methadone as a substitution therapy for opioid dependence. Despite the effectiveness of the methadone maintenance therapy[6], the meta-analytical pooled prevalence for sexual dysfunction among methadone users was 52% (95% confidence interval [CI], 0.39–0.65). In this meta-analysis, hypoactive sexual desire and low libido were the most prevalent sexual dysfunctions compared to other sexual dysfunction, accounting for 51%[7]. Methadone-maintained patients, their partners and clinicians who were interviewed regarding the influence of sexual dysfunction perceived that that sexual dysfunction decreased quality of patient's sexual life [8] and damaged intimate relationships, while at the same time possibly increasing risk of dropout from methadone maintenance therapy prematurely [9] and to use suboptimal methadone dose or other illicit drugs. [10] Management for methadone induced sexual dysfunction remain a challenge for the physicians because the reducing or stopping the methadone in this group of patients may not be always possible. Hence, the physicians need other strategies to manage the sexual dysfunction in this group of patients.

Methadone is the slow-and-long acting opiate agonist that cause the stimulation of mu opiate receptors in the various area of the brain. There are few hypothesis that try to explain the correlation of methadone and sexual dysfunction. One of well known hypothesis was the neuroendocrinologic effects of methadone that exert on the tubero-infundibular and hypothalamus-pituitary-gonadal (HPG) axis. The previous studies found that the patients in methadone therapy had alternation of the prolactin levels compared with the healthy subjects. Hence, the hypothesis that the chronic stimulation of the μ opiate receptors by methadone, alters the functioning of the tubero-infundibular axis and the dopaminergic control of prolactin with the consequential impact on sexual functioning was formulated. [11] A high level of circulating prolactin causes inhibition of gonadotrophin releasing hormone which lowers levels of sex hormone, especially testosterone. Men with low testosterone levels may exhibit a decrease in sexual interest.[12]This is evidenced by aquantitative meta-analysis study, which showed that testosterone, free testosterone and estradiol level was impaired and statistically associated with sexual dysfunction in the patients who were on methadone maintenance therapy.[13] However, in a recent study also showed that there were more than 50% of methadone maintenace therapy patients had sexual dysfunction (55% had erectile dysfunction and

65% had orgasm dysfunction), only 15% of them had hyperprolactinaemia.[14] Therefore, this hypothesis could not solely explain the sexual dysfunction in this group of patients.

The effects of the neurotransmitter dopamine on male sexual behavior have been discussed for centuries. The mesoaccumbens dopamine system has been implicated in the neural processes of sexual motivation in many animal studies.[15] However, the first recognized dopamine-mediated enhancement of sexual behavior in human was when administration of l-dopa (3,4-dihydroxy-l-phenylalanine), the precursor to dopamine, to men suffering from Parkinson's disease resulted in increased libido and sexual potency. [16] In a recent imaging study showed that the methadone maintenance patients has reduced dopamine receptor 2 (D2) in the various part of the brain with the consequences of reduced functioning of the dopaminergic system in brain.[17] There are studies also showed methadone inhibit copulatory behaviour when given either acutely or chronically in animals and decrease socio-sexual interaction, apparently without interfering with locomotion.[18] Therefore, there are researchers proposed to use dopamine agonist such as bromocriptine or dopamine reuptake inhibitor such as bupropion to treat sexual dysfunction in this group patients. There was an open-labelled, quasi-experimental study done by Tatari et al. In 2013 [19], whereby 100mg of Bupropion was administered on 67 methadone maintenance men who had erectile dysfunction for six weeks. In this study, Bupropion significantly improved the erectile function in this group of patients. However, the sample size of that study was small and with many methodological limitations. Hence, I aim to conduct a randomised controlled trial of Bupropion in the treatment of erectile dysfunction among men on methadone maintenance therapy

1.1 Investigational Agent

Bupropion hydrochloride sustained-release (Trade name is Wellbutrin SR™), an antidepressant of the aminoketone class, is an inhibitor of the neuronal reuptake of norepinephrine and dopamine, and does not inhibit the reuptake of serotonin. Its structure closely resembles that of diethylpropion; it is related to phenylethylamines. It is designated as (±)-1-(3-chlorophenyl)-2-[(1,1-dimethylethyl)amino]-1-propanone hydrochloride. The molecular weight is 276.2. The molecular formula is C₁₃H₁₈ClNO•HCl.[20]

Bupropion is extensively metabolized in humans. Three metabolites are active: hydroxybupropion, which is formed via hydroxylation of the tert-butyl group of bupropion, and the amino-alcohol isomers, threohydrobupropion and erythrohydrobupropion, which are formed via reduction of the carbonyl group. The elimination half-life of metabolites are ranged from 20 hours to 37 hours. [20]

1.2 Overview of Non-Clinical Studies

Carcinogenesis : Nodular proliferative lesions of the liver at doses of 100 to 300 mg/kg/day (approximately 2 to 7 times the MRHD on a mg/m² basis) was found in a rat study but not in the mouse study. There were no increase in malignant tumors of the liver and other organs were seen in either study. Bupropion produced a positive response (2 to 3 times control mutation rate) in 2 of 5 strains in the Ames bacterial mutagenicity assay.

Bupropion produced an increase in chromosomal aberrations in 1 of 3 in vivo rat bone marrow cytogenetic studies.[20]

A fertility study in rats at doses up to 300 mg/kg/day revealed no evidence of impaired fertility.[20]

1.3 Overview of Clinical Studies

There was an open-labelled, quasi-experimental study done by Tatari et al. In 2013 [19], whereby 100mg of Bupropion was administered on 67 methadone maintenance men who had erectile dysfunction for six weeks. In this study, Bupropion significantly improved the erectile function in this group of patients (IIEF score improved from 12.79 ± 1.37 to 15.94 ± 2.14). However, the sample size of that study was small and with many methodological limitations.

1.4 Risk / Benefit Assessment

1.4.1 Dose Rationale

In this study, the usual adult target dose for bupropion hydrochloride sustained-release is 300 mg per day, given as 150 mg twice daily. Initiate dosing with 150 mg per day given as a single daily dose in the morning. After 3 days of dosing, the dose may be increased to the 300-mg-per-day target dose, given as 150 mg twice daily. This is based on a phase II, randomized, placebo controlled, adjunctive bupropion sustained-release (SR) on male sexual dysfunction (SD) induced by a selective serotonin reuptake inhibitor. In this study, 117 patients were randomly assigned to receive 12 weeks of bupropion SR 150 mg twice daily. 97.3% of the patients did not complain any adverse effects (AEs), the most commonly reported AEs were headache (8.5%), nasopharyngitis (6.8%), insomnia (6.0%) and dry mouth (6.0%). There were no severe AEs during the trial.[20]

1.4.2 Potential Risk

The potential risks of this study include adverse reactions to bupropion hydrochloride sustained-release. Clinical condition of the subjects will be closely monitored by the study design

1.4.3 Potential Benefit

Methadone induced sexual dysfunction that is experienced by the patients who are receiving study medication may be improved. Patients in the study will receive close psychiatric and medical attention. The potential benefits to the partners include improvement of the marital relationship with the patients

1.4.4 Risk Benefit Ratio

The potential benefits of this study far outweigh the potential risks. Methadone induced sexual dysfunction in this group of patients by far does not have standard treatment. Literature reviews have shown that the lowering or stopping the methadone dosage increase the relapse risk in this group of patients. In contrast, bupropion as an adjunctive treatment was shown to have an early positive effect on the treatment of erectile dysfunction in this group of patients. Patients accepted into the study will receive close medical and

psychiatric monitoring as well as treatment with methylphenidate that has a well-documented safety profile. Patients will be screened prior to admission into the study. The subjects selected for participation will be monitored closely for adverse effects.

2 STUDY RATIONALE

Sexual dysfunction is highly prevalent among methadone maintenance male patients. Previous studies found that sexual dysfunction decreased quality of patient's sexual life [8] and damaged intimate relationships, while at the same time increased the risk of dropout from methadone maintenance therapy prematurely [9]. Although the sexual dysfunction is related to the methadone dose, some of the ex-opioid dependent patients relapsed after their methadone dosage became too low. Worse still, some of them used other illicit drugs, especially stimulants, to boost up their sex function [10]. Currently, there are no standard treatment to treat methadone induced sexual dysfunction. Therefore, we are using bupropion hydrochloride sustained-release to treat methadone induced sexual dysfunction.

